## 3.2 Study Duration, Enrollment, Number of Sites and Project Management

### 3.2.1 Duration of Study

All participants will be enrolled over an 18-24 month period and followed for at least 2 years post-enrollment.

### 3.2.2 Timeline for Subject Enrollment

The timeline for subject enrollment is summarized in Table 6. Children recruited for the ancillary study will be those who are screened for the parent RIVUR study but are found not to have VUR. Therefore, enrollment for the ancillary study will be concurrent with the parent study. The parent study began enrollment in June of 2007 and will enroll children for 18-24 months, depending on enrollment rates. We plan to begin enrollment in October 2007 and finish enrollment in March 2009, three months before enrollment for RIVUR is completed. The numbers in the timeline assume a 10% loss to follow-up per year.

	Year 1			Year 2			Year 3			Year 4			Year 5			
	Apr-Jun	Jul-Sep	Oct-Dec	Jan-Mar	Apr-Jun	Jul-Sep	Oct-Dec	Jan-Mar	Apr-Jun	Jul-Sep	Oct-Dec	Jan-Mar	Apr-Jun	Jul-Sep	Oct-Dec	Jan-Mar
	2008			2009			2010			2011			2012			2013
RIVUR Enrollment																
Baseline visit (n=360)	60	60	60	60	60	60										
6 Month Visit			60	60	60	60	60									
12 Month Visit (n=320)					54	54	54	54	54	54						
18 Month Visit							54	54	54	54	54					
24 Month Visit (n=288)									49	49	49	49	49	49		
Close database and database reconciliation														X	X	
Analysis and Manuscript Preparation															X	X

### 3.2.3 Total Number of Study Sites/ Total Number of Subjects Projected

Participants will be recruited from 3 study sites:

- 1) The CHOP Healthcare Network, which includes the wards of the Main Hospital, the Emergency Department, the Radiology Department, 6 Urology Practices, and 33 primary care practices sharing a common electronic health record in the CHOP Healthcare Network. The outpatient practices of the CHOP Healthcare Network span a large geographic area and provide a wide array of primary care and sub-specialty services. In FY 2004 the CHOP Healthcare Network saw a total of 987,342 outpatient visits. CHOP's four primary care centers and one faculty practice provide health services to more than 20,000 area children. The Hospital has also established a network of 28 regional pediatric practices in Pennsylvania, New Jersey, and Delaware called "Kids First," with 153 physicians and total patient panels exceeding 74,000 covered lives. All 33 of these primary care practices are members of a Practice Based Research Network and share a common electronic health record (EPIC).
- 2) The CHP Healthcare Network, which includes the Primary Care Center (22,300 visits annually), the Emergency Department (60,000 visits annually), 18 suburban affiliated community pediatric sites, the Division of Pediatric Urology, and the hospital wards at CHP.
- 3) The CNMC Healthcare Network, which includes five Children's Health Centers and five subspecialty Outpatient Centers located throughout the Washington-metro area, as well as the Emergency Department and hospital wards at CNMC.

The RIVUR protocol stipulates that CHOP and CHP each enroll 120 subjects into the RIVUR study. We anticipate that CNMC, which is part of a larger network of centers in the RIVUR study (represented on the steering committee by Women and Children's Hospital of Buffalo) will contribute 60 subjects to RIVUR. If randomization results in half of these 300 subjects receiving placebo, then there will be 150 subjects from these 3 study sites in the placebo arm of RIVUR.

The participants in the proposed ancillary study will serve as the comparison group. Each of the sites intends to enroll 120 subjects for a total of 360 subjects in the comparison group. This should not be problematic, even if the study's enrollment period does not overlap completely with RIVUR's, because among children who have had a UTI, approximately 60-70% will not have VUR, so non-refluxing children will outnumber refluxing children by at least 2.5:1. Furthermore, there will be fewer disincentives to enrollment in the ancillary study, as it is observational in nature, involves and does not include randomization to a placebo. For these reasons, we do not anticipate difficulty enrolling 120 subjects per site, even with an anticipated start date up to 1 year into RIVUR's enrollment period.

Combining placebo treated participants from RIVUR and participants in the ancillary study, our sample size will be 510 (150 from RIVUR and 360 from the ancillary study). If, as described in the "Background and Significance" section (1.1), approximately two-thirds of enrolled children will have pyelonephritis and 15-52% of them will develop scars from the index UTI, then approximately 10-35% of children (n=51 to 179) will have some renal scarring during the 2-year study period. This does not take into consideration renal scarring that will develop from recurrent UTIs, which will only serve to increase the proportion of children who have renal scarring at the end of 2 years.

### **3.2.4 Project Management**

#### **3.2.4a Leadership at Participating Sites**

Drs. [name], [name], and [name] (from CHOP, CHP, and CNMC, respectively) will serve as site directors at each of their institutions and will develop and implement all policies, procedures and processes and provide oversight of the research protocol. In these roles, they will be responsible for the implementation of the scientific agenda and will ensure that systems are in place to guarantee institutional compliance with US laws, DHHS and NIH policies including biosafety, human research, data and facilities. [name] will be the Principal Investigator on the grant and in this role will assume responsibility for overall administrative grant management, including maintaining communication among co-investigators and key personnel through monthly meetings, communication with NIH, and submission of annual reports. As site directors at each of their respective institutions, Drs. [name] and [name] will be responsible for his own fiscal and research administration as outlined in the subcontracts established in preparation for the grant proposal. If either of them moves to a new institution, attempts will be made to transfer the relevant portion of the grant to the new institution. In the event that they cannot carry out their duties, a new co-investigator will be recruited as a replacement.

#### **3.2.4b Steering Committee**

The site directors, along with [name] from the Data Coordinating Center, will be members of the Steering Committee for the study. The Steering Committee will communicate once to twice a month, either by phone or in person, to discuss experimental design, data analysis, and all administrative issues. They will work together to discuss any changes in the direction of the research projects and the reallocation of funds, if necessary. The steering committee will also make decisions regarding the involvement in the ancillary study of other sites participating in the parent study (RIVUR) (Figure 6).

[figure not shown]

Figure 6. Organizational Chart

### 3.3 Study Population

This study will enroll approximately 360 children 2-72 months of age. Children of both genders and any race/ethnicity who receive care in the healthcare networks of the study sites will be considered for enrollment. Parents of eligible children will be invited to participate in the study based on the diagnosis of a first or second UTI. Children for whom parents provide consent will be evaluated with a renal ultrasound, VCUG and DMSA scan within 16 weeks of the UTI. The ultrasound and VCUG are routine and the DMSA is increasingly used to evaluate children with UTI. This study will enroll only children, who may be considered a vulnerable population.

#### 3.3.1 Inclusion Criteria

- 1) Age at enrollment 2-72 months. Note that children as young as 1 month may be screened for study.
- 2) Diagnosed first or second  $FIS$  UTI within 120 days (16 weeks) prior to enrollment
- 3) Appropriately treated first or second  $FIS$  UTI
- 4) Parental/guardian permission (informed consent) and if appropriate, child assent.

#### 3.3.2 Exclusion Criteria

- 1) For children less than 6 months of age at randomization, gestational age <34 wks
- 2) UTI diagnosis more than 112 days (16 weeks) prior to enrollment
- 3) Index UTI not appropriately treated
- 4) VUR (Grades I-V) diagnosis by VCUG
- 5) Co-morbid urologic anomalies
  - Hydronephrosis, SFU Grade 4
  - Ureterocele
  - Urethral valve
  - Solitary kidney

- Profoundly decreased renal size unilaterally on ultrasound, (based on 2 standard deviations below the mean for age and length) performed within 112 ( 16 weeks) days of diagnosis index UTI
  - Multicystic dysplastic kidney
  - Neurogenic bladder
  - Pelvic kidney or fused kidney
- 6) History of other renal injury/disease
  - 7) Congenital or acquired immunodeficiency
  - 8) Complex cardiac disease
  - 9) Any known syndromes associated with VUR or bladder dysfunction
  - 10) Unable to complete the study protocol
  - 11) Unlikely to complete follow-up

### 3.3.3 Comparison Group from RIVUR Study

- 1.) **Inclusion: Subjects enrolled in RIVUR study and randomized to placebo.**
- 2.) **Exclusion: RIVUR subjects that have not agreed to future use of their data.**

Subjects that do not meet all of the enrollment criteria may not be enrolled. Any violations of these criteria must be reported in accordance with IRB Policies and Procedures

### 3.3.4 Inclusion of Women and Minorities

We plan to recruit and enroll children that are representative of the gender, racial, and ethnic distribution of children with UTI in the Healthcare Networks of CHOP, CHP, and CNMC. Table 7 summarizes the projected sex and ethnic distribution of children that we will enroll in the study. It is based on the distributions observed among children diagnosed with UTI during a 2-year time period at the three participating study sites (weighted by site).

**Table 7. Sex and ethnic distribution of target population**

	American Indian or Alaskan Native	Asian or Pacific Islander	Black, not of Hispanic Origin	White	Total Racial	Hispanic or Latino	Not Hispanic or Latino	Total Ethnic
Female	1%	3%	26%	49%	79%	8%	71%	79%
Male	0%	1%	8%	13%	21%	3%	18%	21%
Total	1%	4%	34%	62%	100%	11%	89%	100%

## 4 STUDY PROCEDURES

### 4.1 Baseline DMSA Renal Scans

All children enrolled in the study will have a DMSA scan within 2 weeks following enrollment and no more than 16 weeks (112 days) of the index UTI to determine the presence of APN or pre-existent renal scarring. Children will be injected with a dose of 5 mCi TcDMSA per 1.73 m^2 body surface area (minimum dose 1 mCi). High-resolution

magnified images of the kidney will be obtained, including posterior and both right and left posterior oblique projections using a gamma-camera-computer system equipped with a high resolution parallel collimator, between 2-4 hours following injection. Right to left relative function will be calculated by the ratio of right kidney to left kidney counts obtained from the posterior views after background correction. The results will be described quantitatively as the percentage uptake in the right kidney vs. left kidney. Absolute uptakes will not be obtained. Cortical defects at this early DMSA will be defined as focal or diffuse decreased uptake of DMSA with/without loss of contours or cortical thinning with decreased volume. Using criteria established by [name], defects will be classified as APN or pre-existent renal scarring. These cortical defects will be assessed semi-quantitatively by dividing the renal cortex into 12 equal segments (Figure 7). The number of renal parenchyma segments affected will be determined and the grade of scarring will be assigned based on a grading system developed by the Imaging Committee of the RIVUR study during development of that protocol.

Figure 7. Grading system for characterizing extent of renal scarring

Grade	Description
1	1-2 kidney segments affected
2	3-4 kidney segments affected
3	>4 kidney segments affected
4	Global atrophy characterized by a diffusely scarred and shrunken kidney.

These evaluations will be made by two reference nuclear medicine investigators employed through the RIVUR study, including [name] at CNMC. The standardized grading systems will be used by the reference nuclear medicine investigators without knowledge of clinical events or treatment arm. Final diagnosis of disagreements in interpretations will be reconciled by consensual diagnosis. The process for interpreting DMSA scans has been validated (inter and intra-observer reliability measured) and improved as part of an imaging pilot for the RIVUR study.

#### 4.2 Baseline Evaluation

Information on the following potential predictors and confounders of renal scarring and recurrent UTI will be collected during the baseline evaluation:

- 1) **Demographic information** on sex, race, ethnicity, age, sibling order, parental education, and income will be collected.
- 2) **History of index UTI** including type and duration of symptoms prior to antibiotic treatment, highest documented temperature at presentation, documented physical exam findings, antibiotic choice and duration of therapy.
- 3) **Past medical history** including regular medications and chronic conditions will be collected. There will be an age-appropriate evaluation for dysfunctional voiding symptoms based on the Dysfunctional Voiding System Score developed by Farahat et al, and an assessment for constipation using definitions published by the Paris Consensus on Childhood Constipation Terminology (PACCT) Group.

- 4) **Family history** of VUR, UTI, renal scarring, and kidney disease will be collected.
- 5) **Entry examination** will include a general physical examination, blood pressure, height or length, and weight.
- 6) **Laboratory data** from the index UTI will be abstracted from medical records. These include infecting organism and its sensitivity/resistance pattern, information about inflammatory markers, such as peripheral white blood cell count, neutrophil percentage, erythrocyte sedimentation rate, and C-reactive protein.
- 7) **Baseline blood** will be collected and tested for serum creatinine, and Cystatin C (using the same central laboratory as the RIVUR trial). Additional blood will be collected, stored and shipped to the NIH Biosample and Genetics Repositories for future studies.
- 8) **Baseline urine** will be collected, stored and shipped to the NIH Biosample Repository for future studies.
- 9) A **quality of life** instrument will be administered and a parent diary will be distributed.

All data will be entered in electronic case report forms (eCRFs). Optional paper CRFs will be available.

#### 4.3 Monitoring and Evaluations During Subsequent Episodes of Fever

Parents will be educated at the time of their child's enrollment in the study about the potential sequelae of untreated UTI and the benefits of prompt and adequate treatment. They will be instructed to (1) contact primary care providers and study personnel in the event of intercurrent febrile illness, (2) have their child evaluated within 24-48 hours and (3) have a urine specimen obtained to evaluate for the presence of UTI. Additionally, a recent history of fever or other signs or symptoms compatible with UTI will be identified by information obtained during study-initiated phone calls every 2 months. The research nurse or the PI at each participating site will be available to parents of enrolled children via a study-dedicated cellular phone or hospital-based beeper. Primary care providers will be reminded through regular communication and letters about their patient's participation in the study. Specimens for culture will be obtained at the time of febrile illnesses and when children have symptoms localized to the urinary tract. Stringent criteria for recurrent UTI will be identical to those used at study entry. Children with reinfections will be treated with effective antimicrobial therapy as outlined previously and will continue in the study until they complete the study protocol or develop a degree of renal scarring or number of reinfections used in the RIVUR protocol to define treatment failure.

#### 4.4 Phone Contact and Routine Follow-up Visits

Following the protocol established for the parent RIVUR study, parents will be contacted by phone or email every 2 months to ascertain intercurrent illnesses, and children will be seen at routine follow-up visits at 6, 12, 18 and 24 months. The target date of these visits or phone interviews will be determined by the date of enrollment. All interviews and clinic exams will be conducted within 10 days of the target date. If the follow-up schedule must be changed due to illness, geographic relocation or extended vacation, procedures will be followed to document the change in schedule. If a patient misses an appointment, a study

coordinator will contact his/her family by phone or mail to inquire about intercurrent illness. At each study visit an interim history and physical examination will be performed. Dysfunctional voiding will be assessed at the 12 and 24 month visits. Parent diaries will be reviewed at each study visit and quality of life questionnaires will be completed at the 12 and 24 month visits. Measurement of serum creatinine and cystatin-c and urine microalbumin/creatinine will be repeated at the 24-month visit. Urine and blood specimens will be collected again at the 24-month visit for submission to the NIDDK Biosample and Genetics repositories.

#### 4.5 Outcome DMSA Scan

Outcome DMSA renal scans will follow the same procedures and standards of the baseline scan. In general participants will have the outcome DMSA scan performed 24 months after the index UTI. For safety reasons, we will use the criteria developed to define treatment failure for the RIVUR study as indications for performance of an early DMSA scan. Therefore, children whose baseline DMSA scan shows minimal or no scarring (grade 2 or less in each kidney) will have their outcome DMSA scan performed early if they experience the occurrence of 2 recurrent  $\neq$ UTIs or a total of 4 recurrent  $\neq$ UTIs within the study period. The outcome DMSA in these children will be performed approximately 4 months after the last UTI that qualified them as a "treatment failure". Children whose baseline DMSA scan shows grade 3 or higher scarring in either kidney will have a repeat DMSA scan performed at the time of any recurrent  $\neq$ UTI; if additional renal segment involvement (acute pyelonephritis or renal scarring) is observed, then, an outcome DMSA scan will be performed at approximately 4 months following any  $\neq$ UTI. If no additional renal segment involvement is observed, the child will have the outcome DMSA scan performed at 24 months per routine. Finally, children who have a febrile UTI in the first 8 months of the study will have an interim DMSA scan performed at 12 months. If new renal scarring is noted, that child will be considered a treatment failure and the interim DMSA scan will serve as the outcome scan. If a febrile UTI occurs within 8-12 months, the interim DMSA scan will be scheduled 4 months from the interim UTI.

#### 4.6 Indications for Referral to a Pediatric Urologist

For safety reasons, we also will use the criteria developed to define treatment failure for the RIVUR study as indications for referral to a pediatric urologist. Therefore, children whose baseline DMSA scan shows minimal or no scarring (grade 2 or less in each kidney) will be referred to a urologist if they experience occurrence of 2 recurrent  $\neq$ UTIs or a total of 4 recurrent  $\neq$ UTIs within the study period. Children whose baseline DMSA scan shows grade 3 or higher scarring in either kidney will have a repeat DMSA scan performed at the time of any recurrent  $\neq$ UTI; if additional renal segment involvement (acute pyelonephritis or renal scarring) is observed, then, in addition to having the outcome DMSA scan at approximately 4 months following the  $\neq$ UTI, they will be referred to a pediatric urologist.

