Chronic constipation in the toilet trained child, as defined by the Paris Consensus on Childhood Constipation Terminology (PACCT) Group 	
The occurrence of 2 or more of the following during the last 8 days in the toilet-trained child
 
 
• Frequency of bowel movement <math>< 3</math> / week
 
• More than one episode of fecal incontinence / week
 
• Large stools in the rectum or palpable on abdominal examination
 
• Passing of large stools that may obstruct the toilet
 
• Display of retentive posturing and withholding behaviors
 
• Painful defecation
 

Treatment failure:	
Treatment failure is defined by:
 
I. In any participant:

---

- Occurrence of 2 recurrent  $\text{F}_{\text{UTI}}$ s or a total of 4 recurrent  $\text{F}_{\text{SUTI}}$ s within the study period, OR
- Interim 12-month scan shows new or worsening scarring at a site different from the index APN or worsening scarring evidenced by extension of a preexistent scar seen on the baseline DMSA scan (note, the interim scan may serve as the outcome DMSA scan in these participants).

OR

- II. In children with baseline scarring grade 3 or higher:
  - Children whose initial DMSA scan shows grade 3 or higher scarring in either kidney will have a repeat DMSA performed at the time of any recurrent  $\text{F}_{\text{UTI}}$ ; if additional renal segment involvement is observed (APN or scar) compared with the baseline scan, then the child will be categorized as treatment failure and have an outcome DMSA scan at approximately 4 months following the  $\text{F}_{\text{UTI}}$ . If no additional renal segment involvement is observed, the child will continue in the study as assigned.

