## 5.2 Primary Endpoint: Renal Scarring

The incidence and extent of renal scarring will be determined 24 months after the index UTI episode using renal scintigraphy ( $^{99}\text{Tc}$  dimercaptosuccinic acid (DMSA) scan). Children who experience "treatment failure" as defined in the parent study will have the outcome scan approximately 4 months later. Renal scarring will be defined as decreased uptake of tracer associated with loss of contours or cortical thinning. In order to quantify the extent of renal scarring, each kidney will be divided into 12 segments and a five level grading system will be applied (Figure 6). Severe scarring will be defined as the presence of grades 3 or 4 scarring on at least one kidney.

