### 5.3.2 "Treatment Failure"

Although treatment will not be provided as part of this observational study protocol, we will characterize the children in this ancillary study in terms of the criteria used to define treatment failure in the RIVUR study. In any participant, the occurrence of two  $r$ UTIs or a total of four  $F/S$ UTIs during the study period or an interim 12-month scan showing new scarring at a site different from the index APN or worsening scarring evidenced by extension of a preexistent scar seen on the baseline DMSA scan will be classified as a treatment failure. In treatment failure cases where new or worsening scarring is observed on the 12-month DMSA scan, the interim scan may serve as the outcome DMSA scan. Children whose baseline DMSA scan shows grade 3 or higher scarring in either kidney will have a repeat DMSA performed at the time of any recurrent  $r$ UTI. If additional renal segment involvement is observed in comparison with the baseline scan, these children will also be categorized as treatment failure and have an outcome DMSA scan at approximately 4 months following the  $r$ UTI. If no further damage is apparent, they will continue in the study as assigned.

Children whose interim 12-month scan shows new or worsening scarring in comparison to a previous scan will be classified as meeting treatment failure criteria. The interim scan will serve as the outcome DMSA scan in these participants.

---

 Must occur within  $\pm$  24 hours of initiating work-up for UTI.

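### Sections 4.5 and 4.6 withhold the recurrent-UTI trigger for early scan and urology referral from children with baseline grade 3 or higher scarring, against the protocol's own definition of treatment failure

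*Protocol*

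**What the plan says.** **Definition of treatment failure.** The glossary opens its first limb with "In any participant". The limb covers two recurrent febrile UTIs, four recurrent febrile or symptomatic UTIs in total, or new or worsening scarring on the 12-month scan. A second limb, joined by OR, applies to baseline grade 3 or higher: a repeat scan at any recurrent febrile UTI, with failure if more segments are involved. Section 5.3.2 repeats this ("In any participant, the occurrence of two" febrile UTIs, or four in total) and says that grade 3 children with new involvement are also failures. MOP 10.7.1 uses the same text.

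**What failures receive.** Section 5.2 states that children who fail "as defined in the parent study will have the outcome scan approximately 4 months later". Sections 8.2.4a and 8.2.4f promise an early outcome scan and a urology referral. MOP 10.7.4 gives all failures a scan four months after failure. None of these carries a grade limit.

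**Sections 4.5 and 4.6.** Both say that, for safety reasons, they use the RIVUR failure criteria. Section 4.5 then says that "children whose baseline DMSA scan shows minimal or no scarring (grade 2 or less in each kidney) will have their outcome DMSA scan performed early" on reaching the UTI count, and 4.6 says that "children whose baseline DMSA scan shows minimal or no scarring (grade 2 or less in each kidney) will be referred to a urologist" on the same count. For grade 3 or higher, both act only if the repeat scan at a recurrent febrile UTI shows more involvement. Otherwise 4.5 says: "If no additional renal segment involvement is observed, the child will have the outcome DMSA scan performed at 24 months per routine".

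**The concern.** The grade restriction does not follow from the criteria that the two sections invoke. It takes the count trigger away from the children whose kidneys are already worst.

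Sections 4.5 and 4.6 are safety rules, and sections 8.2.4a and 8.2.4f offer the same steps to families and the IRB as risk mitigation. As written, 4.6 and 8.2.4 give different referral answers for the same child, and 4.5 and 5.2 give different scan dates. A site coordinator who works from section 4 would neither refer nor rescan some children whom section 8 says will be referred and rescanned.

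**Working it through.** The check is a comparison of rules, plus one line of arithmetic on timing. The plan states no figure to reproduce. The UTI subscripts in 4.5 and 4.6 did not survive text extraction. They are read as febrile, and febrile or symptomatic, from the legible glossary, MOP 7.4.5.1 and MOP 10.7.4.1. The grade restriction itself is fully legible.

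**Step 1: apply each rule to each type of child.**

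| Baseline grade and course | Failure by definition? | 5.2, 8.2.4a, 8.2.4f | 4.5 and 4.6 alone |
|---|---|---|---|
| Grade 2 or less; 2 febrile or 4 total UTIs | Yes | Early scan and referral | Early scan and referral |
| Grade 3+; febrile UTI with new segments | Yes | Early scan and referral | Early scan and referral |
| Grade 3+; 4 afebrile symptomatic UTIs | Yes (first limb) | Early scan and referral | No early scan, no referral |
| Grade 3+; 2 febrile UTIs, no new segments | Yes (first limb) | Early scan and referral | Acute repeat scans; outcome scan at 24 months; no referral |
| Any grade; new scarring on interim scan | Yes | Referral; interim scan serves as outcome | Scan rule agrees; referral not listed in 4.6 |

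The scan and referral rules conflict in the third and fourth rows. In the fifth row, 4.6 leaves out a referral that 8.2.4a and 8.2.4f cover.

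The third row is the cleanest. No febrile UTI occurs, so the repeat-scan rule never starts, and the 1-year scan also needs a febrile UTI (MOP 7.4.5.1).

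The fourth row is partly a tension inside the definition. The glossary says "If no additional renal segment involvement is observed, the child will continue in the study as assigned" and section 5.3.2 says "If no further damage is apparent, they will continue in the study as assigned". Neither adds that this holds only if no other failure criterion is met.

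**Step 2: difference in outcome-scan date.** Let the qualifying UTI fall at month m, on the same clock as the 24-month scan.

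- Section 5.2 and MOP 10.7.4: scan at m + 4.
- Section 4.5 for these children: scan at 24.
- Gap = 24 − (m + 4) = 20 − m months, and zero from m = 20.

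| Course (grade 3+) | m | Gap = 20 − m (months) |
|---|---|---|
| Fourth afebrile UTI | 8 | 12 |
| Fourth afebrile UTI | 12 | 8 |
| Fourth afebrile UTI | 16 | 4 |
| Second febrile UTI, both after month 12 | 13 | 7 |
| Second febrile UTI, both after month 12 | 15 | 5 |
| Second febrile UTI, both after month 12 | 18 | 2 |

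In the afebrile cases, 4.5 alone provides no study scan in the interval. In the febrile cases the acute repeat scans are still done. A febrile UTI in the first year also brings an interim scan: at month 12 if it falls in the first 8 months, or four months after the UTI (months 12 to 16) if it falls at 8 to 12 months. That shortens the time without a scan. The months chosen are illustrations.

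**The case against.** The best reply is that 4.5 and 4.6 should not be read alone. Both adopt the failure criteria, neither says that only the listed children qualify, and 8.2.4a and 8.2.4f expressly cover all failures. On that reading 4.6 is merely an incomplete list, and the 24-month sentence in 4.5 is a default after one febrile UTI without progression. This is a fair way to rescue the intent. It does not explain why both sections, after invoking the criteria, write a grade limit into them.

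The second reply is operational. Failure status is assigned centrally under MOP 10.7.1, which has no grade limit. The coordinating center requests scans after a febrile UTI or a failure determination (MOP 3.3.1) and notifies the site within 24 hours (MOP 10.7.3). MOP 10.7.4, in a chapter dated later than the protocol, gives every failure a scan at four months. This would probably catch many of these children. Two gaps remain. MOP 7.9.2 sends scan scheduling back to the protocol, where 4.5 and 5.2 disagree. MOP 10.7.3 and 10.7.4 name standard or usual care, not the urology referral promised in section 8.2.4.

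Third, Figures 10.1 and 10.2 are the flow charts for exactly these children and are not shown. They may settle part of the practice, but a manual figure cannot reconcile two protocol sections. By its caption, Figure 10.2 covers children without a febrile UTI in the first year.

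Finally, the clinical effect is limited. The study is observational, radiology reports go to parents and the primary care provider, and UTIs get standard care. That stands, and it bears on size rather than on whether the rules conflict.

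**Conclusion.** The concern holds. Sections 4.5 and 4.6 narrow a criterion that the definition applies to every participant, and for two types of grade 3 or higher child they give different answers from sections 5.2, 8.2.4a and 8.2.4f.

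The number affected cannot be computed, because the documents give neither the rate of baseline grade 3 or higher scarring nor the rate of multiple recurrences. It is likely to be a handful. The any-scar primary endpoint is barely touched, since these children are already scarred at baseline. What is at stake is a stated safety rule, and it should be corrected on that ground.

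The conclusion assumes that the lost subscripts mean febrile, and febrile or symptomatic, as in the glossary. The practical consequences also depend on flow charts that could not be seen.

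**What to change.** - In 4.5 and 4.6, replace the grade-limited wording with a reference to the single definition in the glossary and section 5.3.2, so that the two-febrile or four-total trigger applies to every participant.
- Keep the grade 3 or higher new-segment rule as an additional trigger.
- Make the 24-month default in 4.5, and the sentence about continuing as assigned in the glossary, section 5.3.2 and MOP 10.7.1, conditional on no other failure criterion being met.
- Add interim-scan failures to the referral list in 4.6.

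The cost is a short protocol amendment, one matching line in MOP 10.7.1 and a memo to the three sites. The downside is a few more early DMSA scans, at 69 to 155 mrem each by the protocol's radiation table, and a few more urology referrals. Section 8.2.4 already promises both.
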